#### 2. Establishment of Analysis Set

Efficacy assessment shall use the intention-to-treat (ITT) populations as the analysis sets, and analysis shall be performed on the auxiliary per-protocol (PP) sets. The definition of each analysis set for the assessment of safety, tolerability, and efficacy is as follows:

#### 2.1 Analysis Sets for Safety and Tolerability Assessments

#### 2.1.1 Safety Set

Among all subjects evaluated for their eligibility during the screening period, those subjects whose safety can be assessed after being administered the investigational product shall be included in the safety analysis. The subjects included in the safety analysis shall be analyzed based on the information of the actually administered investigational product. In addition, the demographic data (sex, age, etc.) and background factors (medical history, previous drug treatment history, etc.) shall be analyzed in the safety set.

#### 2.2 Analysis Set for Efficacy Assessment

#### 2.2.1 Intention to treat (ITT) Set

Subjects who have been administered the investigational product and have undergone efficacy assessment at least once shall be included in the ITT analysis set, regardless of protocol violations, compliance with visit schedule, etc.

#### 2.2.2 Per Protocol Set (PPS)

PPS shall include those subjects in the ITT set who have completed the clinical study according to the clinical study protocol without major protocol violations. Subjects who fall under the following shall be defined as PPS. The violation of eligibility in condition number  $\widehat{(1)}$  of PPS shall be determined in a data review meeting prior to

datalock.

- ① Subjects who have not violated the inclusion and exclusion criteria (eligible patients)
- Subjects who have completed all visits

Analysis shall also be performed on PPS by using the auxiliary analysis sets to analyze the sensitivity of the efficacy assessment.

#### 2.3 Subgroup Analysis Population

When conducting assesments for adverse event and efficacy subgroup analysis shall be performed by considering the following items:

- Sex (male, female)
- Age (≤ median, > median)
- Baseline BMI (≤ median, > median)
- Presence or absence of medical history
- Presence or absence of concomitant drugs
- Disease severity (CMTNS-v2) (mild, moderate)

If the subjects within each subgroup are  $\leq$  30%, analysis shall not be performed. For example, if  $\leq$  30% of the total number of subjects is male, no subgroup analysis for sex shall be performed, and whether an analysis should be performed shall be determined in a data review meeting prior to datalock.

#### 2.4 Data Review Meeting

The planned analyses shall be established in a data review meeting prior to datalock and the analysis sets shall be finally determined

Based on the clinical study protocol, SAP, and the major protocol deviation items that occurred during the clinical study which were received from PM, the details of the criteria for analysis set definition shall be prepared as a Definition of Analysis Population (DAP) document. The major deviations considered in the final DAP shall be discussed in the data review meeting and the analysis sets shall be finally determined. The records on the details discussed in the data review meeting prior to datalock shall be collected and a blind data review report shall be prepared.

#### 3. Definitions of Statistical Analysis Variables

#### 3.1 Demographic Information and Comparison of Clinical Characteristics

#### 3.1.1 Demographic Information

Sex, age, height, weight, BMI, smoking history, alcohol consumption history

#### 3.1.2 Medical History Survey (past medical history, current illness)

Medical records on the medical history within 6 months before Visit 1 (screening) were obtained, and all positive/negative results were recorded in detail in the case report form. However, medical history/treatment history related to cancer was surveyed regardless of the time period. New results found at Visit 1 (screening) and Visit 2 (before administration of investigational product) were considered a part of medical history and were not recorded as adverse events. The investigator verified whether the diagnosis of CMT1A has been genetically confirmed for the patient. In the case of medical history, it shall be deemed as past medical history if persistence is "no," and if persistence is "yes," it shall be deemed as current illness.

#### 3.1.3 Previous/Concomitant Medications (Treatment)

All medications and treatments administered within 6 months before Visit 1 (screening) were surveyed. Previous medications and previous treatments shall be defined as all previously collected medications and treatments before Visit 2\*. Concomitant medications and treatments\*\* shall refer to all medications that have been administered at least once starting from Visit 2 and throughout the clinical study. The categories of collected medications and treatments shall follow this definition. The following were also surveyed for each medication:

- \*Prior medications and prior treatments: Start date ≤ Visit 2 (Day 0)
- \*\*Concomitant medications and concomitant treatments: End date  $\geq$  Visit 2 (Day 0) or if ongoing
- Brand name
- Indications for medication administration (reason for administration)
- Dose/strength, administration route, number of administrations
- Start and discontinuation dates of administration (whether to continue when the clinical study is terminated)

#### 3.1.4 Physical Examination

This was performed at Visit 1 (screening), and physical examinations were performed on external appearance, skin, head/neck, chest/lungs, heart, abdomen, urinary/reproductive system, limbs, musculoskeletal system, nervous

system, lymph nodes, and other items. All abnormal findings were recorded in the case report form, and the clinical significance of each finding was assessed.

#### 3.1.5 Electrocardiogram

A 12-lead electrocardiogram was performed at Visit 1 (screening). If there are results from a test performed at the same institution within 4 weeks before Visit 1 (screening), they may serve as a substitute.

#### 3.2 Safety and Tolerability Endpoints

#### (1) Adverse events

Adverse events refer to undesirable and unintentional symptoms (e.g., motion sickness), signs (e.g., enlarged liver), and clinically significant abnormalities (e.g., abnormal laboratory test values), but they do not necessarily must have a causal relationship to the formulation used in the relevant clinical study.

#### Adverse Drug Reactions (ADRs)

Adverse drug reactions (ADRs) are all harmful and unintentional reactions that occur at any dose of the investigational product, and they refer to cases of which the causal relationship to the investigational product cannot be denied.

#### Adverse Events of Special Interest (AESIs)

AESIs are clinically significant unexpected medical reactions known to have been caused by the investigational product, or deemed to be possible risks based on the knowledge regarding the content and/or interactions of the investigational product.

All AESIs that occurred during the clinical study shall be collected in the case report form, and the events described below shall be classified as adverse events of special interest and shall be managed as safety data by the Helixmith PV team.

- 1) Coronavirus infection (COVID-19)
- 2) Local skin reactions (injection site reactions) after administration

#### Serious Adverse Events (Serious AEs/ADRs)

"Serious adverse events/adverse drug reactions" (serious AEs/ADRs) refer to cases that correspond to any one of the following among the adverse events or adverse drug reactions that occur at any dose of the investigational product.

- 1) Death has occurred or a life-threatening situation has developed.
- 2) Hospitalization or prolongation of hospitalization is required.
- 3) Permanent or serious impairment and functional decline have developed.
- 4) Malformation or abnormality has occurred in a fetus.
- 5) Other than the cases in (1) to (4), cases in which drug dependence or abuse has occurred or cases in which other medically significant situations have occurred such as hematologic diseases

The above phrase, "life-threatening situation has developed," refers to an event in which a subject faces an immediate risk of death at the time of AE occurrence.

If a subject visits the emergency room and the duration of treatment exceeds 24 hours, it shall be deemed as satisfying the hospitalization criterion. It shall not be deemed an adverse event or serious adverse event if hospitalization is scheduled prior to the initial administration of the investigational product, or in the case of cosmetic surgery. Elective surgery in the absence of adverse events and its following hospitalization as well as admission to a nursing hospital for the purpose of convalescence shall not be deemed as serious adverse events. However, if hospitalization was not planned or is the result of an adverse event, it shall be deemed as a serious adverse event.

Other than the situations listed above, if situations considered to have medically significant effects on the subjects' safety and health status do occur, the determination on whether the situation corresponds to a

serious adverse event shall be made based on the medical judgments of the physician in charge and relevant specialists, and appropriate actions shall be taken accordingly.

#### **Unexpected Adverse Events**

These are adverse events that differ in terms of the pattern or risk level of the adverse drug reactions compared with available drug-related information such as the investigator's brochure or drug attachments, or those adverse events that are not specified. An expected situation refers to a case in which a previously manifested adverse event is observed when the investigational product is used, while not being accompanied by past medical history or concomitant medications, and the description of which is provided in the investigator's brochure.

#### **Expected Adverse Events**

These are adverse events that have been observed and confirmed in previous clinical studies as well as being described in the available drug-related information such as the investigator's brochure, clinical study protocol, or drug attachments, and even though they do not include cases that are accompanied by past medical history or concomitant medications, the cases in which expected adverse events are repeatedly occur over time due to a specific disease state.

(2) Laboratory tests (general hematology/ general blood chemistry/urinalysis tests)

The laboratory test items are as follows:

- General hematology
  - : WBC, RBC, Hb, Hct, MCV, MCH, MCHC, PLT, ESR, MPV, differential count of WBC (Band neutrophil, Segmented neutrophil, Eosinophil, Basophil, Lymphocyte, Monocyte)
- General blood chemistry test
  - : total protein, albumin, globulin, A/G ratio, cholesterol, total bilirubin, AST, ALT, fasting glucose, BUN, creatinine, estimated GFR, Ca2+, phosphate, Na+, K+, Cl-, CRP, triglyceride, HDL-cholesterol, LDL-cholesterol
- Urinalysis
  - : Color, turbidity, specific gravity, pH, albumin, glucose, ketone, bilirubin, blood, urobilinogen, nitrite, leukocyte esterase, microscopy (RBC, WBC, casts)

#### (3) Vital signs

Vital signs including blood pressure (measurement was taken with the subject in a sitting position after resting for at least 10 minutes prior to measurement), temperature, heart rate per minute, and respiratory rate per minute were measured. The measurement results were recorded in the subjects' case report forms. This was performed at Visit 1 (screening) and throughout the clinical study every time a subject made a visit (on the drug administration days consisting of Visits 2, 3, 4, and 5, it was performed both prior to administration and  $2 \pm 1$  hours after administration). However, if there is a subject with abnormal findings in the test at Visit 3 (Day 14), a follow-up test may be performed at Day 30 at the discretion of the principal investigator.

#### 3.3 Efficacy Endpoints

Severity of disease

This was measured using Charcot-Marie-Tooth Neuropathy Score version 2 (CMTNS-v2) and the functional disability scale (FDS).

#### CMTNS-v2

Charcot-Marie-Tooth Neuropathy Score version 2 (CMTNS-v2) is a measurement tool for evaluating the severity of disease. Measurements shall be taken for 9 items which include 3 items for disease symptoms, 4 items for signs, and 2 items for neurophysiological testing. The severity of disease shall be classified according to scores as mild (≤10), moderate (11 to 20), and severe (>20). This clinical study shall target mild to moderate patients. This was performed at Visit 1 (screening), Visit 2 (Day 0), and Visit 7 (termination visit, Day 270) (performed prior to administration at Visit 2 [Day 0]).

#### FDS

The functional disability scale (FDS) assessed a patient from 0 to 8 points as shown below depending on the patient's mobility. The assessment day was at Visit 2 (Day 0), Visit 4 (Day 90), Visit 6 (Day 180), and Visit 7 (termination visit, Day 270) (assessment was performed prior to administration at Visit 2 [Day 0] and Visit 4 [Day 90]).

0=normal;

1=cramps and fatigability;

2=inability to run;

3=possible unaided;

4=with cane;

5=with crutch;

6=with walker;

7=wheelchair;

8=bedridden.

#### (2) Lower limb function

Changes in lower limb function were assessed using the overall neuropathy limitation score (ONLS) and the 10-meter walk test (10MWT).

#### ONLS leg scale

The overall neuropathy limitation scale (ONLS) is a tool for measuring the activity level of patients with peripheral neuropathy. It is scored by separately categorizing arms and legs. Measurement shall be performed only on legs in this clinical study. The measurement day was at Visit 2 (Day 0), Visit 4 (Day 90), Visit 6 (Day 180), and Visit 7 (termination visit, Day 270) (measurement was performed prior to administration at Visit 2 [Day 0] and Visit 4 [Day 90]).

#### 10MWT

This is a test that measures the time required for a subject to walk 10 meters. A subject shall be made to walk at a desired speed while wearing shoes. The subject shall be allowed to use an assistive device that the subject normally uses, if any. The subject shall be made to walk a corridor that is 14 meters long, and the time taken to walk 10 meters shall be measured with a stopwatch provided by the sponsor (time taken to pass 10 meters excluding 2 meters each for the starting and ending portions). The assessment day was at Visit 2 (Day 0), Visit 4 (Day 90), Visit 6 (Day 180), and Visit 7 (termination visit, Day 270). (Assessment was performed prior to administration at Visit 2 [Day 0] and Visit 4 [Day 90]). The starting point at 2 meters, the point for ending measurement at 12 meters, and the point for end of walking at 14 meters shall be marked in advance along the corridor.

#### (3) Fatty infiltration level of lower limb muscles

The fatty infiltration level of the leg muscles injected with the investigational product shall be assessed with an MRI leg scan.

#### MRI leg

The muscles of lower limbs were imaged, and the fatty infiltration level of the leg muscles injected with the investigational product were measured and evaluated as fat content value (%) at one level for each muscle. The test days were at Visit 2 (Day 0) and Visit 7 (termination visit, Day 270) (performed prior to administration at Visit 2 [Day 0]). Considering the schedule, etc., of the institution, it was performed optionally at the early termination visit and unscheduled visits, and the details including the reasons for not performing the test were recorded in the case report form.

#### (4) Nerve regeneration potential

Nerve conduction studies including compound motor nerve action potential (CMAP), compound sensory nerve action potential (SNAP), and nerve conduction velocity (NCV) were performed.

The test days were at Visit 2 (Day 0) and Visit 7 (termination visit, Day 270) (performed prior to administration at Visit 2 [Day 0]).

#### (5) HGF antibody production by Engensis (VM202)

The presence or absence of HGF antibody (anti-HGF Ab) in blood was verified with the ELISA method. A preliminary assessment was performed on whether antibody production is correlated between the subject group determined to have increased muscle mass and improved function, and the subject group not determined as such.

However, if antibodies in blood were not produced in any of the subjects, the results were not presented.

The antibody test for hepatocyte growth factor was performed at Visit 2 (Day 0) and Visit 7 (termination visit, Day 270) (performed prior to administration at Visit 2 [Day 0]).

#### 4. Statistical Analysis Method

#### 4.1 General Principles of Statistical Analysis

Since this is a phase 1/2a clinical study and the number of subjects is small, the data from the treatment period and the follow-up period shall be descriptively compared and reviewed. For continuous data, descriptive statistics (number of subjects, mean, standard deviation, median, maximum, minimum) shall be presented, while frequencies and percentages shall be presented for categorical data.

If necessary or if comparisons are possible, statistical test shall be performed. The p-value shall be presented up to 4 decimal places, and a two-tailed test shall be performed under a significance level of 0.05. In addition, for descriptive statistics, numbers with values below the decimal point shall be presented up to 2 decimal places.

#### 4.2 Adjustment for Covariates

Not applicable.

#### 4.3 Handling of Dropouts or Missing Values

For missing values due to early termination of subjects, they shall not be imputed and shall be analyzed using the available data set.

Replacements shall be made as shown below if the start date and end date, start date/surgery date, and onset date and recovery date are not collected for prior/concomitant medications (treatment), medical history, and adverse events, respectively. However, if "year" is missing, the date shall not be replaced and shall be handled as a missing value.

Table 1. Handling of missing date values

	Missing	Handling of Missing Value	Exceptions	
Start Date	If only "day" is missing	Replace with 01 (1st day).	If the corresponding date started in the same year and month of Day 0 (first administration day), set it as Day 0.	
	If "day / month" are missing	01 (1st day) / JAN (January)	If the corresponding date started in the same year of Day 0 (first administration day), set it as Day 0.	
	If only "day" is missing	Replace with the last day of the corresponding month	If the end date handled as a missing value falls after the	
End Date	If "day / month" are missing	31 (31st day) / DEC (December)	study termination date or before the study start date, set it as the study termination date.	

Not applicable.

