- 7) Retrospective biomarker study: Blood samples are collected at Day 0, Day 90, Day 180 and Day 270 (or early termination visit) for retrospective biomarker study of CMT. Collected samples will be processed according to detailed procedure in a separate protocol. CMT 질환의 후향적 생물학적 표지자 연구를 위하여 Day 0, Day 90, Day 180, Day 270 (또는 조기 종료 방문)에 혈액을 수집한다. 수집된 혈액은 별도의 연구계획서에서 구체적인 연구방법에 따라서 진행될 것이다.
- 8) Chest X-ray (PA): At Visit 1 (screening), chest PA X-ray shall be performed to verify whether active tuberculosis is present. The results within 1 month (30 days) before Visit 1 may be used.
- 9) Urinalysis: The laboratory test items are as follows:
 - Color, turbidity, specific gravity, pH, albumin, glucose, ketones, bilirubin, blood, urobilinogen, nitrite, leukocyte esterase, microscopy (RBC, WBC, casts)
- 10) Urine or serum pregnancy test At Visit 1 (screening), urine or serum pregnancy tests shall be performed in females of childbearing potential (from post-menarche females to females ≥ 50 years of age within 1 year of menopause, or from post-menarche females to females < 50 years of age within 2 years of menopause). However, patients with surgical menopause (hysterectomy, bilateral oophorectomy, etc.) or who underwent sterilization surgery (bilateral tubal ligation, bilateral tubectomy) may be excluded. Menopause refers to the state after 1 year of amenorrhea.
- 11) Electrocardiogram: The electrocardiogram to be performed at Visit 1 (screening) may use results within 4 weeks before Visit 1 (screening).
- 12) Concomitant medications survey: All medications and treatments administered within 6 months before Visit 1 (screening) shall be surveyed. Previous medications and previous treatments shall be defined as all previously collected medications and treatments before Visit 2 (first administration of investigational product). Concomitant medications and

treatments shall refer to all medications that have been administered at least once starting from Visit 2 (first administration of investigational product) and throughout the clinical study. The categories of collected medications and treatments shall follow this definition. Whether the medications and treatments being administered should be continued shall be investigated at each visit.

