7.4.3 Reporting, collection, and recording of AEs

The principal investigator must educate the sub-investigator and subjects or representatives of the subject about all adverse events that may occur after the administration of the investigational product and educate them to report all reactions that occur after administration.

- All AEs that occur from administration of investigational product to follow-up visits (until end of the clinical trial) are collected. However, if a sign, symptom, or disease that occurred before the administration is worsened after the administration, it shall also be considered an AE.
- An AE must be reported including the name of the AE, start date and end date, severity, actions related to investigational product, progress, causality with the investigational product, remedial treatment, and whether it is an SAE.
- When documenting an AE, the investigator uses a comprehensive diagnosis or symptom name using standard medical terminology instead of each symptom or sign.
- 4) AEs are observed for the study period of nine months (day 0 to 270). If an AE or SAE that occurs within the nine-month follow-up period is not resolved within this period, follow-up shall be conducted until the AE is resolved.

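### SAP Table 1 moves an imputed end date that falls before study start to the study termination date, so a medication that had certainly stopped is counted as concomitant (minor)

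*SAP*

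**What the plan says.** SAP 4.3 completes partial dates for three kinds of record. For medications and treatments, medical history and adverse events, in that order, it covers the "start date and end date, start date/surgery date, and onset date and recovery date". If the year is missing, nothing is imputed.

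For an end date with the day missing, Table 1 says "Replace with the last day of the corresponding month". With day and month missing it uses 31 December of the known year. One exception covers both rows: a completed end date that falls after the "study termination date or before the study start date, set it as the study termination date". The SAP does not define the study start date.

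SAP 3.1.3 gives the test that uses this date: "Concomitant medications and concomitant treatments: End date" on or after Visit 2 (Day 0), or ongoing. Prior use is tested on the start date alone (on or before Day 0), so a record can be both prior and concomitant. The same section also defines concomitant in words, as use at least once from Visit 2 on, and adds: "The categories of collected medications and treatments shall follow this definition". Protocol 6.1, note 12, has the same definition: concomitant medications and "treatments shall refer to all medications that have been administered at least once starting from Visit 2".

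**The concern.** Capping a late completed date at study termination makes sense. Moving an early one forward does not. The completed date is already the latest stop compatible with what was recorded, so a value before study start leaves no uncertainty for a cautious rule to cover. A program that follows Table 1 exactly would therefore break the verbal definition that SAP 3.1.3 says the categories must follow.

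Two outputs are at stake: the concomitant medication and treatment tables in SAP 4.6.3, and the subgroup by concomitant drug use in SAP 2.3 and 4.9, which applies to adverse events and efficacy.

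**Working it through.** The plan has no figure to reproduce here; the check is of the date logic and of its size at the planned n.

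**Inputs**

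- L, the completed end date: month-end, or 31 December of the known year (SAP 4.3, Table 1).
- S, study start (undefined); T, study termination; D0, Visit 2 (Day 0).
- Exception: if L > T or L < S, then E = T; otherwise E = L.
- Concomitant if E ≥ D0 or ongoing; prior if start ≤ D0 (SAP 3.1.3).
- Collection: medications and treatments from the 6 months before Visit 1 onwards (SAP 3.1.3; Protocol 6.1, note 12).
- n = 12 (SAP 1.4.1).

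**Step 1: logic.** The true stop is never later than L. If L < S and S ≤ D0, the true stop is before D0, so by the verbal definition the record is not concomitant. The exception sets E = T, and T ≥ D0 for any dosed subject, so the record is always classed as concomitant. An enumeration agrees. It used 366 Day 0 dates, study start 0, 1, 30 or 60 days before Day 0, and every month or an unknown month of two years. All 25,921 of the 25,921 combinations with L < S came out as concomitant. This confirms the logic; it says nothing about frequency.

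**Step 2: example.** Assumed dates: Visit 1 on 20 Jun 2020, D0 on 6 Jul 2020, T = D0 + 270 days = 2 Apr 2021.

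| Recorded end | L | S read as Visit 1 | S read as Day 0 | Second condition deleted |
|---|---|---|---|---|
| May 2020 | 31 May 2020 | moved to 2 Apr 2021: concomitant | moved to 2 Apr 2021: concomitant | 31 May 2020: prior only |
| Jun 2020 | 30 Jun 2020 | kept: prior only | moved to 2 Apr 2021: concomitant | 30 Jun 2020: prior only |

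The May record moves by 306 days. Under the Visit 1 reading the drug stopped earlier is concomitant and the one stopped later is not. A record ending in July 2020 gives L = 31 Jul 2020 and is concomitant with or without the exception. The stop there is truly uncertain, and the deletion leaves that record alone.

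**Step 3: reach.** With the day missing, L < S only if the stop month is before the month of study start. With day and month missing, it requires a stop year before the year of study start. Both are outer bounds, because drugs stopped more than 6 months before Visit 1 are not collected. Day-missing stops therefore come from roughly the last six or seven calendar months before screening. If study start is a subject-level date, a year-only record is reached only where the look-back, or the time from screening to Day 0, crosses 1 January.

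**Step 4: size at n = 12.** Each moved record adds one concomitant case. The subject count rises only if the subject has no other drug in that row, and then by 1/12 = 8.3 points. For the overall line, with the Clopper-Pearson 95% intervals of SAP 4.6.3, the two extremes are:

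- 0/12 (0 to 26.5%) becomes 1/12 (0.2 to 38.5%).
- 11/12 (61.5 to 99.8%) becomes 12/12 (73.5 to 100%).

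For the subgroup, a group of 3/12 = 25.0% fails the 30% criterion and one of 4/12 = 33.3% passes. One false flag therefore changes the result at only two splits: from 4 to 3 subjects without concomitant drugs (the analysis is lost) and from 9 to 8 (it is gained).

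**The case against.** The strongest reply is that this may never happen. The number of affected records is not in the documents and may be 0, and data validation (Protocol 9.2) may resolve most partial dates. The verbal definition in SAP 3.1.3 is correct and would justify correcting a wrong flag. The data review meeting settles the planned analyses (SAP 2.4) and decides whether a subgroup analysis is run. All of this stands as to weight. It does not remove the error, because neither data validation nor the meeting is written to correct a derived flag.

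Four stronger readings are tempting, and the documents do not support them:

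- *The clause distorts adverse event or medical history dates.* For medical history the rule covers start and surgery dates only. For adverse events, Protocol 7.4.3 says "All AEs that occur from administration of investigational product to follow-up visits (until end of the clinical trial) are collected", so a recovery before study start should not arise.
- *Every earlier stop is caught.* The 6-month look-back limits what is in the data.
- *The study start date must be defined.* Its reading decides which records are moved today, but once the condition is deleted the term decides nothing in Table 1.
- *The start-date rule must be repaired as well.* The concomitant test uses no start date. A start set to Day 0, to the first of the month or to 1 January passes the prior test alike for these records.

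**Conclusion.** Wrong as written; severity minor. For every record it reaches, the second condition classes as concomitant a medication or treatment that had certainly stopped before the trial. This holds under any reading of study start that falls on or before Day 0.

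Affected records remain correctly in the prior table; the error is the additional entry in the concomitant table. The subgroup consequence needs a subject with no other concomitant drug, and that analysis is exploratory. A reader might infer that the safety or efficacy conclusions are at risk. They are not: the primary and main secondary analyses use no medication end date. The example dates are assumed, and no frequency is claimed.

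**What to change.** In the End Date exception of Table 1, delete the second condition, the one for dates earlier than study start. The rule would then read: *if the imputed end date is later than study termination, use the study termination date; otherwise keep the imputed date.* No definition of study start is then needed. The cost is one phrase in the SAP and one branch in the derivation code.

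Optional, for date order only: do not let an imputed start date be later than the end date. For a start with only the year known, Table 1 says "If the corresponding date started in the same year of Day 0 (first administration day), set it as Day 0". In the example, a start recorded as 2020 becomes 6 Jul 2020, which is 36 days after a kept end of 31 May 2020. The same already happens with complete end dates: a known end of 15 May 2020 lies 52 days before that start. For these records, correcting it changes no planned table.
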